12.0 CRITERIA FOR THERAPEUTIC RESPONSE/OUTCOME ASSESSMENT

The primary outcome of this study is the difference in body surface area (BSA) (Appendix I-II) of non-sclerotic and superficially sclerotic cutaneous cGVHD between ruxolitinib treated side and vehicle treated sides of the face/body at study completion (day 28 ± 3 days). Clinical assessment at all study visits, including baseline BSA will be performed by a dermatologist ([name], [name], [name], or [name]), and subsequently BSA will be calculated via photos by a single bone marrow transplantation hematologist.

Criteria for evaluation of clinical efficacy

No validated instruments for clinical assessment of chronic cutaneous GVHD exist[24]; we propose to use efficacy criteria that have been previously developed for evaluation of cutaneous T-cell lymphoma[25]. The body surface area (BSA) is the primary endpoint of efficacy. Secondary endpoints of efficacy include: Physician's Global Assessment of Clinical Condition (PGA), or the Composite Assessment of Index Lesion Severity (CAILS) grading scales are the secondary end points of efficacy[25]. The PGA will be the investigators' subjective assessment of the overall improvement or worsening in disease compared with the baseline assessment[25].

The CAILS assessment will generate a separate composite score for the treated and non-treated sides of the study participant. The assessment data to generate the composite score will be generated from case report form from the study visit. The treatment and vehicle sides of the body will be assessed for erythema, scaling, pruritus and size. For erythema, scaling and pruritus, the following grading system will be used.

CAILS Grading Tool for Erythema, Scaling, Pruritus [25]

MEMORIAL SLOAN KETTERING CANCER CENTER
IRB PROTOCOL

Scale	Grade
0	No evidence of sign or symptom
1	Intermediate interval
2	Mild: less than average presentation of sign or symptom
3	Intermediate interval
4	Moderate: average disease presentation of sign or symptom
5	Intermediate interval
6	Severe: >25% worse than average severity of sign or symptom
7	Intermediate interval
8	Very severe: the near worst severity of sign or symptom

*Intermediate intervals 1, 3, 5, and 7 serve as midpoints between the defined grades of 0, 2, 4, 6 and 8.

An estimate for the % involvement of the right and left areas will be assessed on scale of 0 to 11 as follows:

CAILS Grading Tool for BSA Involvement

Grade	BSA within marked treatment area on each side
0	0
1	>0 and \leq 2
2	>2 and \leq 4
3	>4 and \leq 6
4	>6 and \leq 8
5	>8 and \leq 10
6	>10 and \leq 12
7	>12 and \leq 14
8	>14 and \leq 16
9	>16 and \leq 18
10	>18 and <20
11	20

Composite Assessment of Index Lesion Disease Severity (CAILS): Signs and Symptoms and BSA Grade for Each of the 2 Selected Sides[25] (Extracted by unblinded Research Study Assistant from Physician-completed Appendix V)

Clinical Sign and Size	Non-Treated Area	Treated Area
Erythema	a (range 0-8)	e (range 0-8)
Scaling	b (range 0-8)	f (range 0-8)
Pruritus	c (range 0-8)	g (range 0-8)
Size (BSA)	d (range 0-11)	h (range 0-11)
Total	a+b+c+d (range 0-35)	e+f+g+h (range 0-35)

Separate summary scores for the treated and non-treated sides of the face/body will be created by summing $\sum(a-d)$ and $\sum(e-h)$, respectively. We will calculate a ratio of the day 28 assessment total score to baseline assessment total score for the treated and non-treated sides of the participant. We

**MEMORIAL SLOAN KETTERING CANCER CENTER
IRB PROTOCOL**

will evaluate the difference in the ratios between the treated and non-treated sides of the face/body for each study participant.

Physician's Global Assessment of Clinical Condition (PGA)[25]

Grade	Description	Response
0	Completely clear: no evidence of disease (100% improvement)	Clinical Complete Response
1	Almost clear: very significant clearance (>90% to <100%); only traces of disease remains	Partial Response
2	Marked improvement: significant improvement ($\geq 75\%$ to <90%); some evidence of disease remains	
3	Moderate improvement: intermediate between slight and marked improvement ($\geq 50\%$ to <75%)	Stable Disease
4	Slight improvement: some improvement ($\geq 25\%$ to <50%); however, significant evidence of disease remains	
5	No change: disease has no changed from baseline condition ($\pm <25\%$)	Progressive Disease
6	Worse: disease is worse than at baseline evaluation by $\geq 25\%$ or more	

All patients who complete the day 28 +/- 3 days study visit will be eligible for the primary outcome of the study. The primary outcome of this study is the difference in body surface area (BSA) of non-sclerotic and superficially sclerotic cutaneous cGVHD between ruxolitinib treated side and vehicle treated sides of the face/body at study completion (day 28 visit). Assessment for BSA involvement, PGA, and CAILS will be made by a single dermatologist during the patient encounter. The dermatologist will record an estimate of involved BSA, PGA, and CAILS for both sides of the body in a blinded fashion. The CAILS score will be subsequently calculated by research study assistant (RSA), as described above, and the dermatologist and hematologist will be blinded to that score. In addition, clinical images will be taken of the treatment and placebo sides of the body at each patient visit to additionally document BSA involvement. The clinical evaluation, by the dermatologist, will be used for the efficacy assessment.

The secondary outcomes of this study are: (1) The difference in the Physician's Global Assessment of Clinical Condition (PGA) of non-sclerotic and superficially sclerotic cutaneous cGVHD between ruxolitinib treated side and vehicle treated sides of the face/body at study completion (day 28 visit); (2) The difference between the ratios of the day 28 CAILS total score to baseline CAILS total score of non-sclerotic and superficially sclerotic cutaneous cGVHD between ruxolitinib treated side and vehicle treated sides of the face/body at study completion; (3) Difference in the body surface area (BSA), Physician's Global Assessment of Clinical Condition (PGA), and the objective Composite Assessment of Index Lesion Severity (CAILS) of non-sclerotic and superficially sclerotic cutaneous cGVHD between ruxolitinib treated side and vehicle treated sides of the face/body at study completion (day 14 visit); (4) The difference in patient-reported outcomes between the side of the face and body treated with topical ruxolitinib cream versus the contralateral side treated with twice daily vehicle at day 14 visit and day 28 visit using the adapted National Cancer Institute Patient-Reported Outcomes version of the Common Terminology Criteria for Adverse Events (PRO-CTCAE™) questionnaire; (5) The difference in chronic cutaneous non-sclerotic and superficially

**MEMORIAL SLOAN KETTERING CANCER CENTER
IRB PROTOCOL**

sclerotic GVHD BSA between the sides of the face/body treated with topical ruxolitinib and vehicle by measuring the agreement of blinded independent physician's review of standardized photography of the right and left sides of the face and body respectively performed at day 28 visit; (6) The safety and tolerability of topical ruxolitinib by physical examination and adverse event reporting; (7) Accrual, retainment and compliance with therapy

13.0 CRITERIA FOR REMOVAL FROM STUDY

Patients will be removed from the study (and will not be replaced) if:

- They develop an adverse event necessitating discontinuation of topical interventions.
- They require greater than 14 days off therapy due to a treatment-related adverse event.

Patients will be removed from the study and replaced if:

- They enroll in an alternate systemic clinical trial which prohibits concurrent topical clinical trial participation.
- They choose to withdraw consent for continued participation.
- Death occurs.

All patients who receive ruxolitinib and report using the treatment will be evaluable for toxicity.

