2.0 OBJECTIVES AND SCIENTIFIC AIMS

Primary Objective:

- To obtain preliminary efficacy estimates of ruxolitinib 1.5% cream for the treatment of non-sclerotic and superficially sclerotic chronic cutaneous GVHD at day 28 as determined by the body surface area (BSA) of the GVHD rash on the side of the face/body treated with topical ruxolitinib cream versus contralateral side treated with vehicle at day 28 visit when applied beginning on day 1.

Secondary Objectives:

- To obtain preliminary efficacy estimates of ruxolitinib 1.5% cream for the treatment of non-sclerotic and superficially sclerotic chronic cutaneous GVHD at day 28 as determined by the Physician's Global Assessment of Clinical Condition (PGA) of the

MEMORIAL SLOAN KETTERING CANCER CENTER IRB PROTOCOL

GVHD rash on the side of the face/body treated with topical ruxolitinib cream versus contralateral side treated with vehicle at day 28 visit when applied beginning on day 1.

- To obtain preliminary efficacy estimates of ruxolitinib 1.5% cream for the treatment of non-sclerotic and superficially sclerotic chronic cutaneous GVHD at day 28 as determined by the objective Composite Assessment of Index Lesion Severity (CAILS) of the GVHD rash on the side of the face/body treated with topical ruxolitinib cream versus contralateral side treated with vehicle at day 28 visit when applied beginning on day 1.
- To obtain preliminary efficacy estimates of ruxolitinib 1.5% cream for the treatment of non-sclerotic and superficially sclerotic chronic cutaneous GVHD at day 14 as determined by the body surface area (BSA), Physician's Global Assessment of Clinical Condition (PGA), and the objective Composite Assessment of Index Lesion Severity (CAILS).
- Compare the difference in patient-reported outcomes between the side of the face and body treated with topical ruxolitinib cream versus the contralateral side treated with twice daily vehicle at day 14 visit and day 28 visit using the adapted National Cancer Institute Patient-Reported Outcomes version of the Common Terminology Criteria for Adverse Events (PRO-CTCAE™) questionnaire
- Compare the difference in chronic cutaneous non-sclerotic and superficially sclerotic GVHD BSA between the sides of the face/body treated with topical ruxolitinib and vehicle by measuring the agreement of blinded independent physician's review of standardized photography of the right and left sides of the face and body respectively performed at day 28 visit

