14.0 BIOSTATISTICS

Target sample size is 24 patients, wherein 12 patients will be randomized to topical ruxolitinib to right side and 12 patients to the left side, with placebo cream on contralateral side. For each side of the face/body, non-sclerotic and superficially sclerotic chronic cutaneous GVHD BSA, PGA, and CAILS will be assessed in real-time by the study dermatologist observer blinded to the treatment status. The methodology for the real-time BSA calculation is available in Appendix I,II. The efficacy endpoint for the primary objective will be the difference in body surface area (BSA) as recorded by the dermatologist of non-sclerotic and superficially sclerotic cutaneous cGVHD between the topical ruxolitinib and vehicle treated sides of the face/body at study day 28. In this pilot study, we are utilizing three different measures to assess efficacy to qualitatively evaluate which works best for the clinician within the context of the patient visit. The bone marrow transplantation oncologist will subsequently calculate the BSA via total body photographs taken during the visit. Maximum BSA for topical ruxolitinib application will be 20% of overall BSA. All BSA, PGA, and CAILS assessments performed at study days 14 ± 3 days and study day 28 ± 3 days will be performed by the study dermatologist in real-time and serve as the data for the efficacy analysis. All BSA will also be calculated virtually by one bone marrow transplantation hematologist in review of total body photographs performed during visit, blinded to treatment, but will not contribute to efficacy assessments. Participants will only be included in the primary endpoint analysis if they complete the 28 ± 3 days assessment. Descriptive statistics and graphical methods will be employed to evaluate participant characteristics and the distribution BSA, PGA, and CAILS differences at each evaluation time point. Paired t-tests will be performed to assess differences in BSA. In addition, since the overall area treated may vary slightly between participants, we will use linear regression with the difference between treatment and control areas at day 28 as the dependent variable, and the total

**MEMORIAL SLOAN KETTERING CANCER CENTER
IRB PROTOCOL**

treatment area BSA as the independent variable. Regression coefficients along with 95% confidence intervals will be reported for this treatment area adjusted difference.

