The primary aim is to assess the efficacy of ruxolitinib 1.5% cream for the treatment of non-sclerotic and superficially sclerotic chronic cutaneous GVHD at day 28 visit. This is a pilot study. With the average body surface area for male and female adult cancer patients has been estimated to be 1.9m² and 1.7m², respectively[26]. Using an average BSA of 1.8m² (18,000 cm²) for our mixed sample; if we treat, on average, 5.0% BSA per participant, we expect to have equivalent areas of 0.09m² or 900cm² of treatment and control areas per participant.

Table. Effect size calculations for the minimum detectable difference in area between treatment and control sides of the participant based on varying levels of correlation between treatment and control areas within participant.

Effect Size	Difference in area between treatment and control areas (cm ²)	Control area (cm ²)	Treatment area (cm ²)	SD of the difference	SD Control area	Correlation between treatment and control areas
-0.5972	-400.6	900	499.4	670.8	500	0.1
-0.5972	-377.7	900	522.3	632.5	500	0.2
-0.5972	-353.3	900	546.7	591.6	500	0.3
-0.5972	-327.1	900	572.9	547.7	500	0.4
-0.5972	-298.6	900	601.4	500	500	0.5
-0.5972	-267.1	900	632.9	447.2	500	0.6
-0.5972	-231.3	900	668.7	387.3	500	0.7
-0.5972	-188.8	900	711.2	316.2	500	0.8

So, based on these estimates, if we select lesional areas on a patient equivalent to 5% BSA (which is roughly 900cm² for both treatment and control sides), and we have an estimated common standard deviation of 500, with 80% power, a two-sided test, an alpha level of 5%, and a correlation between treatment and control areas of 0.4, we can expect to detect a 327.1cm² difference between treatment and control areas at the day 28 evaluation. The effect size calculation is based on a paired t-test. Since we do not have any pilot data for these calculations, the estimate for the standard deviation that utilized for these estimates comes from experience with conditions with a similar presentation. The Table above lists the expected differences between treatment and control areas based on a range of correlations.

Secondary endpoints include:

1. Physician's Global Assessment of Clinical Condition (PGA) at day 28

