The difference in the PGA score of non-sclerotic and superficially sclerotic cutaneous cGVHD between the topical ruxolitinib and vehicle treated sides of the face/body will be calculated. The Wilcoxon signed rank test will be used to assess differences in these paired assessments for the day 28 assessment.

MEMORIAL SLOAN KETTERING CANCER CENTER IRB PROTOCOL

2. Composite Assessment of Index Lesion Severity (CAILS)

The difference between the ratios of the day 28 CAILS score to baseline CAILS score of non-sclerotic and superficially sclerotic cutaneous cGVHD between ruxolitinib treated side and vehicle treated sides of the face/body at study completion. We will use descriptive statistics to describe the distribution of the difference in CAILS ratios between treated and vehicle sides of the body. The difference in ratios will be assessed using a paired t-test.

3. Efficacy at day 14

Little is known about the efficacy of this treatment in this patient population. As a secondary aim, we will assess efficacy at the 14 day visit as we described for the primary aim of the study using paired t-tests and linear regression to control for potential differences in overall treatment areas between study participants.

4. Patient-reported Outcomes

Patient reported outcomes measured by the NCI Patient Reported Outcomes-Common Terminology Criteria for Adverse Events (PRO-CTCAE™) for each side of face/body affected by GVHD rash; a Likert-scale patient-reported assessment of change in the treated areas has been appended to adapt the PRO-CTCAE™ for this study. PRO-CTCAE™ instrument will be scored as ascribed by methods published for this instrument. Overall summary measures and subdomain measures will be summarized using descriptive statistics. To evaluate differences in the paired responses, for the overall PRO-CTCAE score and for each of the subdomain scores, the Wilcoxon signed rank test will be used.

5. Agreement between GVHD BSA Measurements

GVHD BSA measurements will be evaluated during the patient visit by a dermatologist, and by an additional bone marrow transplant physician using digital clinical images captured during the patient visit. The GVHD BSA assessments for both evaluations will be visually assessed using scatterplots of the two independent assessments and compared using Lin's concordance correlation coefficient.

6. Safety and Tolerability

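### The primary day-28 BSA analysis keeps only completers, and no analysis retains leavers; the estimate may be biased, in either direction, if leaving is related to the side-to-side difference

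*Combined protocol and SAP*

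**What the plan says.** Section 13.0 has two removal lists. Patients who stop because of an adverse event, or who are off therapy for more than 14 days for a treatment-related one, are removed and not replaced. The second list opens with "Patients will be removed from the study and replaced if" and gives three reasons: withdrawal of consent, death, and a move to another trial ("They enroll in an alternate systemic clinical trial which prohibits concurrent topical clinical trial participation").

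Section 14.0 then sets the primary analysis population: "Participants will only be included in the primary endpoint analysis if they complete the 28 ± 3 days assessment". Section 12.0 gives the same rule for the primary outcome. The closing paragraph of section 14.0 applies it to efficacy evaluability in general.

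The primary test is a paired t-test on the side difference, with a supporting regression on treated area. On size, section 14.0 says "Target sample size is 24 patients", and "12 patients will be randomized to topical ruxolitinib to right side and 12 patients to the left side". Sections 4.1 and 16.0 count 10 and then 14 evaluable participants for the two interim analyses, which also adds to 24.

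BSA is measured on both sides at day 14, and for that visit "we will assess efficacy at the 14 day visit as we described for the primary aim of the study using paired t-tests and linear regression". The plan does not use day-14 BSA to inform a missing day-28 value. It names no all-randomised efficacy set, no missing-data method and no sensitivity analysis for non-completers. Retention is described at each time point.

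**The concern.** The primary objective in section 2.0 is worded as a comparison within the patient: "side of the face/body treated with topical ruxolitinib cream versus contralateral side treated with vehicle at day 28 visit when applied beginning on day 1". A natural reading is the effect in patients who start the creams. A completer-only mean describes those who stay to day 28, and the two differ if staying is related to the side difference.

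The protocol gives some reason to think it might be. Section 6.1 requires other topical treatment and phototherapy to stop on Day 0. Section 6.2 lists their use up to Day 28, and changes in systemic therapy for skin GVHD, as exclusions. A patient whose rash is not controlled therefore has a reason to withdraw or to seek a systemic trial, and these are two of the three replaceable reasons.

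What is at stake is the preliminary efficacy estimate, which is the stated product of this pilot. With 24 patients, a few leavers can move it.

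**Working it through.** **1. The plan's own figure.** Inputs from section 14.0: n = 24, SD 500 cm² per side, "with 80% power, a two-sided test, an alpha level of 5%, and a correlation between treatment and control areas of 0.4".

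- SD of the difference = 500 × √(2 × (1 − 0.4)) = 547.7 cm².
- The noncentral t distribution with 23 degrees of freedom gives 80.0% power at a standardised effect of 0.5972.
- 0.5972 × 547.7 = 327.1 cm². The plan's figure is reproduced.
- Standard error with 24 completers = 547.7/√24 = 111.8 cm².

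**2. Simple bound.** Assume 24 completers average a 327.1 cm² benefit and k excluded leavers have no side difference. The mean over all starters is 327.1 × 24/(24 + k), so completers overstate it by k/24.

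| k | All-starter effect (cm²) | Overstatement (cm²) | Overstatement (k/24) |
|---|---|---|---|
| 1 | 314.0 | 13.1 | 4.2% |
| 2 | 301.9 | 25.2 | 8.3% |
| 3 | 290.8 | 36.3 | 12.5% |
| 4 | 280.4 | 46.7 | 16.7% |

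If leavers have half the effect, the overstatement for k = 2 is 12.6 cm². If they have the same effect, it is zero.

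**3. Leaving that depends on the day-14 difference.** Assumptions, none of them from the plan:

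- Day-14 and day-28 differences are bivariate normal with SD 547.7 and correlation ρ of 0.5 or 0.7.
- The log-odds of leaving rise by 1 or 2 per SD of a poorer day-14 difference (odds × 2.7 or × 7.4).
- Leaving is 8.5%, 12.5% or 15%.

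Let m be the amount, in SDs, by which completers' mean day-14 difference is better than that of all starters. Completer bias at day 28 = ρ × 547.7 × m. Percentages are of 327.1 cm².

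| Leaving | Slope | m | Bias, ρ = 0.5 | Bias, ρ = 0.7 |
|---|---|---|---|---|
| 8.5% | 1 | 0.078 | 21 cm² (6.5%) | 30 cm² (9.1%) |
| 8.5% | 2 | 0.124 | 34 cm² (10.4%) | 47 cm² (14.5%) |
| 12.5% | 1 | 0.112 | 31 cm² (9.4%) | 43 cm² (13.1%) |
| 12.5% | 2 | 0.173 | 48 cm² (14.5%) | 67 cm² (20.3%) |
| 15% | 1 | 0.133 | 36 cm² (11.1%) | 51 cm² (15.5%) |
| 15% | 2 | 0.203 | 56 cm² (17.0%) | 78 cm² (23.8%) |

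Against the standard error, the extremes are 21.3/111.8 = 0.19 and 78.0/111.8 = 0.70.

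In simulated trials of the same scenarios (4,000 each, enrolling to 24 completers), an estimate that also used leavers' day-14 data had bias of at most about 1.6% of the effect. Its standard error was about 107 to 114 cm², against 106 to 113 for completers. With leaving unrelated to response, both methods were unbiased to within 1%.

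**4. Direction.** Assume 10% to 30% leaving, with log-odds of 0.5 to 1.0 per SD of the named day-28 quantity. The shift in the completer mean is:

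- driven by a poor side difference: 27 to 138 cm² too favourable;
- driven by the ruxolitinib-side area: 15 to 76 cm² too favourable;
- driven by the vehicle-side area: 15 to 76 cm² too unfavourable;
- driven by average severity of both sides: about zero.

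**5. Limit of the remedy.** If leaving depends on the day-28 difference itself, completer bias is 547.7 × m, or about 13% to 34% of the effect over the cases in step 3. The estimate using day-14 data then keeps about 53% to 79% of it. For example, with 12.5% leaving, slope 1 and ρ = 0.5, it is 14.3% against 18.7% for completers.

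**The case against.** A reader might infer that poor responders are swapped for completers, so that the estimate is biased in favour of ruxolitinib. The documents do not support this. None of the three replacement reasons is defined by response. Both sides leave together and patients are blinded to side, so rash that is bad overall is not enough: leaving must be related to the side difference. If patients leave because the vehicle side is bad, the bias runs against ruxolitinib. Open-label cream after day 28 is also an incentive to stay (offered to all in sections 4.2 and 15.2, to responders in section 9.0).

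A reader might also infer that day-14 data are discarded and the selection is hidden. Day-14 BSA has its own secondary analysis, although the closing paragraph of section 14.0 leaves it unclear whether a non-completer's day-14 values enter it. Retention is a secondary endpoint, so attrition will be visible even though the analysed number stays near 24.

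The leaving rates are weakly grounded. The 8.5% equals the share in study 203 (section 11.0, 17 of 199) who stopped drug for adverse events. Section 13.0 does not replace such patients, though they too drop out of the primary analysis if they miss day 28. No patient in studies 201 or 202 discontinued for an adverse event. The 12.5% and 15% rates and the slopes are assumptions.

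The words in section 2.0 about application from day 1 may only fix when treatment starts, and section 12.0 openly defines eligibility by completing day 28. The bias in step 3 is also below one standard error, and this is a pilot.

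All of this stands, and it limits the claim to a possible bias of unknown size and sign. It does not supply the missing piece, which is any analysis showing whether the completer estimate is sensitive to those who left.

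**Conclusion.** The point holds in a limited form. The primary estimate excludes everyone without a day-28 assessment, and nothing in the plan retains them. This may bias the estimate, in either direction, only if leaving is related to the ruxolitinib-minus-vehicle difference. The exclusion is the cause; replacement only maintains the number analysed.

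The plan gives no dropout rate, so the size is not known. With 8.5% to 15% leaving, more often after a poor day-14 difference, the overstatement is about 7% to 24% of 327.1 cm², or 0.2 to 0.7 standard errors. It is zero if leaving is unrelated to the difference. That is modest beside the sampling error of 24 patients. It still merits a change, because the estimate is the purpose of the study and the data for a check are already collected.

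**What to change.** - **Section 13.0:** state that data collected from removed patients up to leaving, whether or not they are replaced, stay in the efficacy data set unless the patient refuses their use.
- **Section 14.0:** add a repeated-measures model of the per-patient side difference in BSA (ruxolitinib minus vehicle) at days 14 and 28, with a separate mean for each visit and unstructured covariance, in all randomised patients with at least one post-baseline BSA. Report its day-28 mean difference and 95% CI beside the completer paired t-test. With complete data the two give the same day-28 mean difference.
- **Section 14.0:** say whether non-completers enter the day-14 analysis, and list all leavers with time and reason. Report deaths separately, because for them the model implies a day-28 value that does not exist.

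The cost is wording in two sections, one more model and one listing, with no new visits, assessments or patients. The model has limits. It removes the bias only if leaving depends on observed day-14 data; about half to four-fifths remains if leaving depends on the unseen day-28 difference. Patients lost before day 14 still contribute nothing.
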